18.2 Consumer Information Leaflet

CIL Table of Contents - Page 2

CIL Pages 3-5

How to Take Opili.

Take 1 tablet at the same time every single day (and no later than 3 hours from the time you took your pill the day before).

Never skip your daily pill.

- Never take a break between packs. When you finish one pack (all 28 pills), you should start the next pack the following day.
- Take Opill® every single day, even when you have your period, or if you have spotting or bleeding between periods.
- · Do not skip pills even if you do not have sex very often.

To start using Opill*:

- · You can start your first pack on any day.
- If you are switching from another birth control pill, vaginal ring, or patch, start taking Opill[®] the day after you stop the other method.
- You must take your daily pill at the same time of day every single day.
- You must use a condom (or another barrier method) every time you have sex during the first 2 days (48 hours).

What if I am late taking my pill?

Less than 3 hours late:

 Don't worry. Take 1 pill immediately and go back to taking your pill at your usual time the following day.

More than 3 hours late OR you missed one or more pills:

- Take 1 pill immediately, as soon as you remember.
- Then, go back to taking your pill at your usual time. This
 means you may take 2 pills in 1 day.
- For example, if you usually take your pill at night, but forget and remember in the morning, take 1 pill when you remember and take 1 pill again at the usual time that night.
- You must use a condom (or another barrier method) every time you have sex during the 2 days (48 hours) after you restart Opill*, because it takes 2 days to start working again.
- Take a pregnancy test or talk to a doctor if your period is late after missing any pills in the last month.

What if I vomit or have severe diarrhea within 4 hours of taking my pill?

- Use a condom (or another barrier method) every time you have sex for the next 2 days (48 hours) because the medicine may not have been fully absorbed.
- ---The next-day, take your daily-pill-at your usual-time.-

to Take Opill On Time

- Choose a convenient time of day. It is best to link this to something you already do at the same time every day. For example, when you wake up or when you brush your teeth.
- Set an alarm. Consider using your smartphone to set a daily alarm, and using the reminder stickers included in your pack.
- Buy a new pack of Opill* a few days before finishing the pack, so you can start the next pack on time.

18

3

4

CIL Pages 6-8

What if I am taking other medicines or herbal products?

Talk to a doctor or pharmacist if you are taking or start to take any of the following, as these may make Opill* less effective:

- Certain drugs to treat:
 - Seizures (barbiturates, carbamazepine, oxcarbazepine, phenytoin, topiramate, primidone)
- Tuberculosis (rifampicin, rifabutin)
- Pulmonary hypertension (bosentan)
- HIV / AIDS
- St. John's Wort (or any herbal products containing hypericum perforatum)

What if I have taken an emergency contraceptive before starting Opili⁸?

- Talk to a doctor or pharmacist if you have taken an emergency contraceptive in the past 5 days.
- Opill® should not be used for 5 days after using the emergency contraceptive ella® (which contains ulipristal acetate). This might reduce the ability of both Opill® and ella® to prevent pregnancy.
 Also, use a condom (or another barrier method) every time you have sex until your next period.

What if I have sudden or severe abdominal pain in my lower belly?

Contact a doctor immediately.

You may have an ectopic pregnancy (a fertilized egg implanted in the wrong place).

What if I become pregnant while taking Opill®?

- Stop taking this product and talk to a doctor if you get pregnant while taking Opili*.
- Signs that you may be pregnant might include: missed periods, tender breasts, feeling nauseous, fatigue, and/or needing to urinate urgently or more frequently.
- Take a pregnancy test or talk to a doctor if your period is late after missing any pills in the last month, if you have not had a period for 2 months, or if you think you may be pregnant.

What if I get migraines while using Opill®?

If you start having migraines with aura (heodoches that start with changes in vision) or your migraine headaches get worse, talk to a doctor, as some women with migraine may be at increased risk of stroke.

What if I develop yellowing of skin or eyes while using Opill*?

Stop use and ask a doctor if you develop the following rare symptoms -yellowing of the whites of your eyes or skin (especially with fever, tiredness, loss of gopetite or dark colored urine).

What Could Happen to Youir Periods While Taking Opill,?

What changes in my menstrual period are normal while using Opill®?

Most changes to periods are to be expected.

Continue taking Opill* exactly as directed, even if you have the following changes in your periods:

- Your periods may be less or more frequent, shorter or longer, lighter or heavier than before you started Opill*. You may also have some spotting or bleeding between periods.
- . Some women stop having periods while taking Opill*.
- Take a pregnancy test or talk to a doctor if your period is late after missing any pills in the last month, if you have not had a period for 2 months, or if you think you may be pregnant.

What changes to my period are NOT expected when using Opill⁴?

Talk to a doctor while continuing to take this product every day even if you experience any of the following:

- You had unexplained vaginal bleeding between your periods before you started this product.
- You repeatedly have bleeding that is brought on by sex.
- Your menstrual period lasts more than 8 days or is. _____
 unusually heavy.

- 8

CIL Pages 9-10 and Cover Page

What type of birth control is Opill*?

- · Opill* is a progestin-only pill (POP).
- Opill* contains the hormone progestin but does not contain estrogen, so it is different than the commonly used combined birth control pill, which contains both estrogen and progestin.
- Every one of the 28 pills in your blister pack contains the active ingredient, so you must take one pill every day with no breaks.

How effective is Opill® at preventing pregnancy?

- As with any birth control method, Opill* does not prevent pregnancy all the time. Opill* will work best if you take it exactly as directed.
- In 8 US clinical trials, approximately 98 out of 100 sexually active women who used Opill[®] for a year did not become pregnant in that time.

What if I decide I want to get pregnant?

 If you decide you want to become pregnant, simply stop taking Opill®. Opill® will not delay your ability to get pregnant.

Is it okay to use Opill® if I'm breastfeeding?

Yes. Opilit is safe and effective in breastfeeding women.
 Small amounts of progestin may pass into the breast milk; however, no adverse effects have been found on either breastfeeding performance or infant health.

What types of side effects may I expect while using Opill*?

- · When used as directed, Opill* is safe and effective.
- The most common side effect is changes in menstrual periods (bleeding). See previous section 6.
- Less common side effects may include headaches, dizziness, nausea, increased appetite, abdominal pain, cramps or bloating.

What if I still have questions about Opill®?

If you have questions or need more information, call our toll-free number, 1-800-XXX-XXX, or visit our website at www.XXXX.com.

10

consumer information leaflet

[figure not shown]
What You Need to Know

[figure not shown]
Before you use Opill®, read this information carefully and take Opill® exactly as directed.

Keep this leaflet as it contains important information.

46446

CIL (Five Panel, Foldable)

18.3 Reminder Card

Front

Back

# 1. Introduction

Opill® (norgestrel 0.075 mg) is proposed for an Rx-to-OTC (over-the-counter) switch. This combined Self-Selection (SS) / Actual Use Trial (AUT) was intended to be conducted to demonstrate appropriate consumer selection and use behavior as guided by OTC labeling when using the product in the absence of a physician or other learned intermediary.

Due to technical issues with the e-diary application, the study was terminated shortly after the study was initiated, resulting in a sample size that is statistically insufficient to analyze the Primary and Secondary Endpoints as well as the Other Analyses described in Section 9.3 of the protocol. As such, only analyses relating to subject safety, including the number of pregnancies observed over the course of the study, will be completed for this study.

# 2. Trial Objectives

The objective of this study was to evaluate the adequacy of the proposed OTC labeling to guide the behavior of subjects in an OTC-like setting when selecting and using Opill®; however, only the safety outcomes will be reported on for this study due to the early termination of the study.

# 3. Trial Design

This was an observational, open-label, multi-center, 16-week study designed to create as much as possible an OTC-like environment in which participants made an initial self-selection and purchase decision about Opill® based only on their reading of the outside of the package including the DFL. Qualified participants who chose to do so purchased the study medication, left the study site and used the product on their own, guided by the OTC labeling. The study was designed to assess if, when and how subjects use the medication in an OTC-like environment.

It is important to note that none of the information gathered at screening, enrollment, or during the 16-week study period was only discussed with subjects at the End-of-Study interview.

## 3.1 Naturalistic Design

This was a multi-center trial conducted in a simulated OTC environment. Study characteristics and procedures were designed to make it as naturalistic as possible. Some of the key naturalistic elements included the following:

- There were minimal exclusionary criteria imposed on participants, making this trial nearly an all-comers study to mimic the likely OTC population.
- The study was conducted in retail pharmacies, representing typical locations where consumers now commonly purchase OTC medicines (adult and adolescent subjects) and women's health clinics (adolescent subjects).
- The proposed OTC packaging and labeling was the only product information provided to participants during the study. Participants only reviewed the outer packaging including DFL at the initial visit. Study staff did not provide any

additional information or encouragement regarding product selection at that visit. Staff did not answer participant questions about the study medication and instead referred subjects to the labeling. However, any questions related to the "Ask a doctor or pharmacist before use" section of the DFL that were asked of study staff in their capacity as healthcare provider or pharmacist were recorded.

After purchasing the study product, participants took the package with them when they left the site. The package included the outer packaging, and, inside the package, the consumer information leaflet (CIL), a reminder card (which highlights the key messages about directions for use from the DFL) and study medication.

# 3.2 Eligibility Criteria

## 3.2.1 Self-Selection Phase / Initial Enrollment Visit

In order to enroll a sample as representative as possible of the likely OTC consumer population, the study inclusion criteria were defined as broadly as it is feasible. Subjects were required to meet the following initial screening study inclusion criteria:

- 1. Able to read, speak and understand English
- 2. 12 years of age or older
- 3. Can see well enough to read information on the label
- 4. Another member of the respondent's household has not participated in this study
- 5. Consumer or someone else in the household does not work for a market research or advertising company, public relations firm, news organization, pharmacy or pharmaceutical company, medicine manufacturer, as a healthcare professional, or as part of a healthcare practice, managed care or health insurance company, trained or worked as a healthcare professional or market research professional (eliminated for reasons of confidentiality and increased awareness of medicines and their labels)
- 6. Has not participated in any research studies about health-related products in the past 12 months
- 7. Has not participated in a clinical trial in the past 12 months
- 8. Has never participated in a study about over-the-counter birth control medicines

# 3.2.2 Use Phase Exclusion Criteria

All subjects who agreed to participate in the study and attended the initial enrollment visit at the site were asked to make a self-selection and purchase (or use) decision. Subjects presenting with any of the following were not included in the use phase of the study (i.e., were not allowed to purchase and use study medication though their self-selection decision and desire to purchase was recorded):

- 1. Unwilling to purchase study medication (pharmacy sites)
- 2. Unwilling to be dispensed study product for use (clinic sites)
- 3. Unwilling to provide informed consent
- 4. Unwilling or unable to provide contact information

- 5. Unwilling to state that the product is for their own use and no one else's
- 6. Premenarchal females
- 7. Pregnant
- 8. Male
- 9. Known allergy to norgestrel or inactive ingredients.
- 10. History of any cancer

Additionally, subjects must have met all of the following study inclusion criteria to be eligible for enrollment into the use phase of the study:

- Evidence of a personally signed and dated informed consent form indicating that the subject (or a legal guardian) has been informed of all pertinent aspects of the study.
- Willing and able to comply with the initial enrollment visit, planned phone calls and other study procedures, and the end of study visit.

Subject eligibility was reviewed and documented by the Investigator or his/her designee before subjects were allowed to be dispensed the study medication and begin the use phase of the study.

## 3.3 Sample Size Determination

For the purposes of this AUT, sample size was set at approximately 900 purchasers (use phase participants). Given that subjects were responding to recruitment aimed at those interested in an OTC birth control medicine, most subjects who chose to purchase the study product were expected to actually use the product during the study.

Assuming approximately 900 purchasers, if 80% of those purchasers used the product within the study period, that would yield an actual user population of approximately 720. Allowing for a further 20% loss to follow-up would yield a measurable user population of approximately 576.

Because AUTs are not hypothesis-testing comparative trials, study sample size was designed to allow for adequate evaluation of key endpoints across all participants and among several subgroups. As the analysis of AUTs typically focuses on estimating the proportion (and associated 95% confidence intervals) of correct behavior for individual endpoints, sample size is most often based on the number of participants needed to constrain the confidence interval (CI) to a limited range. As an illustration, for this study, assuming an 85% correct behavior to any single endpoint (of course, the CI depends on the actual point estimate and is calculated based on the data), a sample of 720 participants would constrain the CI to  $\pm 2.8\%$ . Table 1 provides the 2-sided 95% CI for various sample sizes around a point estimate of 85%.

#### Table 1 Two-sided 95% CIs for Various Sample Sizes Around 85% Point Estimate

	N=900 a	N=720 b	N=576°	N=135 d
95% CI around a point estimate of 85%	+/-2.5%	+/-2.8%	+/-3.2%	+/-7.2%

#### a Purchasers

- b User population (allowing for 20% non-users)
- $^{\rm c}$  User population (allowing for 20% loss-to-follow up)
- d Low literacy subjects

## 3.4 Randomization

There was no randomization in this study.

## 4. General Statistical Considerations

## 4.1 General Principles

Statistical analyses of the data will be performed by PEGUS Research using the SAS System for Windows v 9.4 (SAS Institute, Cary, NC). All analyses performed in this study will be descriptive.

Frequencies and percentages will be presented for categorical data, mean, standard deviation (SD); median, and range will be presented for numerical data. Percentages will be rounded to one decimal place. The category of missing data will be displayed only if there are actually missing values. Frequencies, percentages and 2-sided 95% CIs will be calculated using the exact method.

## 4.2 Handling of Withdrawn Subjects

For subjects that chose to withdraw at any point during the study, an attempt was made to collect End-of-Study (EOS) information and the reasons for the subject's early termination. Data gathered prior to subject withdrawal and any ongoing data collection will be included in the analysis for completed questions, unless the subject withdrew consent or requested otherwise. Subjects who did not complete the study will be described in a disposition table. Any subjects who withdrew their consent or were determined to be lost to follow-up will be described in the disposition table as well. Withdrawn subjects were not replaced.

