5.5 Subject Withdrawal (Early Termination)

If a subject notifies study staff of their intention to withdraw from the study early, the clinical interviewer will attempt to complete the next scheduled interim interview (unless the subject withdraws consent for disclosure of future information). An EOS interview will also be conducted with any subject who discontinues or withdraws consent prior to Week 16. This interview will attempt to collect the EOS information and the reasons for the subject's early termination. These subjects will also be asked to perform and report the results of the EOS self-administered pregnancy test, and to return materials to the site where an additional self-administered pregnancy test will be performed.

Subject participation may be terminated by an investigator during the study for any of the following reasons:

- Significant protocol violation
- AEs, including serious adverse events (SAEs)
- Pregnancy
- Physician decision
- Subject's request
- At the discretion of the Investigator or designee if s/he feels that study discontinuation is necessary to protect the subject, or that there are unmanageable factors that will interfere significantly with the study procedures and/or the interpretation of results.

Any such subjects will be asked to return any unused study medication (and empty packaging), e-diary devices where applicable, and will be precluded from purchasing additional study medication. Data collected up to the point of withdrawal will be retained and used as appropriate in the data analysis. Ongoing data collection will be allowed if applicable (such as for AE follow-up), unless the subject requests otherwise.

Subjects may withdraw from the trial at any time at their own request, or they may be withdrawn at any time at the discretion of the Investigator or Sponsor (or Sponsor designee) for safety or behavioral reasons, or the inability of the subject to comply with the protocol required schedule of study visits or procedures at a given study site.

If a subject refuses contact for scheduled follow-up calls, any effort made to contact the subject will be documented. In any circumstance, every effort will be made to determine and document subject outcome, if possible. The investigator will inquire about the reason for withdrawal, request the subject to return all unused IP and empty packaging, request

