the subject to participate in a final telephone interview, if applicable, and follow up with the subject regarding any unresolved AEs.

[figure not shown]
A subject may be declared lost to follow-up if, during the study, the available contact information is determined to be incorrect and no other information is available. Every attempt will be made to contact lost to follow-up subjects, including three phone call attempts and a letter sent via USPS. Subjects whose status is withdrawn, lost to follow-up, withdrawal due to an AE or withdrawal from the study for other reasons will be recorded in the study database.

If a subject wishes to stop participation in the study, the Investigator/interviewer will document the reason for withdrawal, ask the end of treatment questions where possible and follow up with the subject regarding any new or unresolved AEs, request that the subject conduct the at home EOS pregnancy test and instruct the subject to return all unused IP and any empty packaging. Data collected up to the point of withdrawal will be retained and used as appropriate in the data analysis.

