12.3 Subject Information and Consent

All parties will ensure protection of subject personal data and will not include subject names or other identifiable data in any reports, publications, or other disclosures, except where required by law. Explicit permission to gather sensitive data will be sought and documented prior to any data collection. No personally identifiable information (PII) will be retained following the study for subjects that either did not pass the screening phase or who do not qualify for the use phase of the study, or choose not to sign consent. Any data collected after explicit permission is granted will be retained as anonymous study data for use by the sponsor.

The informed consent documents must be in compliance with ICH GCP, local regulatory requirements, and legal requirements, including applicable privacy laws.

The informed consent documents used during the informed consent process must be reviewed by the sponsor, approved by the IRB/IEC before use, and available for inspection.

The investigator, or a person designated by the investigator, will obtain informed consent from each subject before dispensing of study medication. Informed consent documents will be presented electronically, and signatures gathered digitally, however, all consent procedures (including obtaining informed consent from a parent or legal guardian, if necessary) will be conducted in person. An archived copy of the signed informed consent document will be made available to subjects digitally.

All subjects who are classified as children according to local laws and regulations will be required to have parental consent for participation in the study as is dictated in 21 CFR 50 subpart D. However, please note the definition of a child, according to 21 CFR 50.3(o) is as follows: "Children means persons who have not attained the legal age for consent to treatments or procedures involved in clinical investigations, under the applicable law of the jurisdiction in which the clinical investigation will be conducted." In many states, adolescents seeking contraception do not need parental consent for

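### SAP 4.2 lets withdrawal of consent remove adverse events and pregnancies already recorded, in a report that covers only safety

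*SAP*

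**What the plan says.** SAP 4.2 (Handling of Withdrawn Subjects) states: "Data gathered prior to subject withdrawal and any ongoing data collection will be included in the analysis for completed questions, unless the subject withdrew consent". The exception continues with a second trigger, so that in full it reads "unless the subject withdrew consent or requested otherwise". On reporting, the section adds: "Any subjects who withdrew their consent or were determined to be lost to follow-up will be described in the disposition table as well".

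Protocol 5.5 (Subject Withdrawal) treats the two kinds of data separately. On data already in hand it says, in two places: "Data collected up to the point of withdrawal will be retained and used as appropriate in the data analysis". On later data it says: "Ongoing data collection will be allowed if applicable (such as for AE follow-up), unless the subject requests otherwise". It also plans contact at exit: "An EOS interview will also be conducted with any subject who discontinues or withdraws consent prior to Week 16". It then adds: "These subjects will also be asked to perform and report the results of the EOS self-administered pregnancy test".

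Protocol 12.3 (Subject Information and Consent) gives a general retention rule: "Any data collected after explicit permission is granted will be retained as anonymous study data for use by the sponsor".

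The SAP limits the report to safety, including pregnancies (SAP 1, 6.2.2 and 6.2.3). SAP 6.2.4.1 takes in every event that began or worsened after treatment, and SAP 6.2.4.2 describes every pregnancy reported during the study. SAP 5 defines the Safety Population by signature of the consent document and makes no exception for consent withdrawn later.

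**The concern.** Withdrawing consent ordinarily stops further collection. It does not by itself decide whether data collected while consent was in force stay in the analysis, so a plan has to settle that point explicitly. SAP 4.2 settles it by a shared exception that, read plainly, reaches back to data already gathered. It does not say that it is departing from the protocol.

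The stakes are higher than usual because adverse events and pregnancies are all that remains to be reported. Listing consent-withdrawers in the disposition table shows that they existed but not what happened to them. Under protocol 7.9, a pregnancy found during treatment goes to the sponsor as an SAE and as an exposure-during-pregnancy report. The same pregnancy could therefore be in the sponsor's safety records and absent from the study report.

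**Working it through.** The plan gives no figure to reproduce, so the main check is a comparison of the texts.

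**1. Grammar of SAP 4.2.** The sentence has two subjects (data gathered before withdrawal, and ongoing collection), one verb (inclusion in the analysis) and one trailing exception. Nothing ties the exception to the second subject alone. A narrower intent is possible, but the sentence does not express it.

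**2. Comparison by type of data.**

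| Data | Protocol 5.5 | SAP 4.2 as worded |
|---|---|---|
| Collected up to withdrawal | Retained and used as appropriate; no exception for withdrawn consent | Included, except where consent was withdrawn or the subject asked otherwise |
| Collected afterwards | Allowed, unless the subject asks otherwise | Same exception as above |
| Exit interview and pregnancy test after consent is withdrawn | Requested | Excludable |

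Protocol 5.5 also has an interim-interview provision that speaks of withdrawing consent to disclose future information, so its language there looks forward.

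**3. Comparison within the SAP.** SAP 6.2.4.1 and 6.2.4.2 are unqualified, and the Safety Population in SAP 5 keeps everyone who signed consent. SAP 4.2 is the specific rule for withdrawn subjects. No sentence says which prevails, so a programmer could follow either and claim to comply.

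**4. The exit test.** Protocol 9.3.3.6 counts a confirmed positive test within 12 days of the end of the use phase as a pregnancy. Protocol 5.5 asks women who withdraw consent to take such a test. SAP 4.2 could leave the result out even when the woman chose to give it.

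**5. Illustration of size.** All counts here are assumed. Let n be the number of users, a the number with an adverse event, and k the number removed from both numerator and denominator.

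- Lowest reported rate, if every removed woman had an event: (a − k)/(n − k).
- Highest reported rate, if none did: a/(n − k).

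With a true rate of 30%:

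| n | a | k = 1 | k = 2 |
|---|---|---|---|
| 20 | 6 | 5/19 = 26.3% to 6/19 = 31.6% | 4/18 = 22.2% to 6/18 = 33.3% |
| 50 | 15 | 14/49 = 28.6% to 15/49 = 30.6% | 13/48 = 27.1% to 15/48 = 31.3% |
| 100 | 30 | 29/99 = 29.3% to 30/99 = 30.3% | 28/98 = 28.6% to 30/98 = 30.6% |

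With 5 of 100 users removed and other true rates:

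- 10%: 5/95 = 5.3% to 10/95 = 10.5%
- 30%: 25/95 = 26.3% to 30/95 = 31.6%
- 50%: 45/95 = 47.4% to 50/95 = 52.6%

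For pregnancies, if the only case was in a removed woman, the reported count falls from 1 to 0.

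**The case against.** The strongest reply is that SAP 4.2 is a general rule, while the retained outcomes have their own sections, and those favour inclusion. SAP 6.2.4 covers all events and all reported pregnancies, and the Safety Population has no exclusion for later withdrawal. On that view this is an unharmonised clause, not a plan to drop safety data. It is true that the SAP states no such aim. But the sections conflict and nothing ranks them, so the point stands.

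Second, the protocol is less firm than it looks. Its retention sentences say data are used as appropriate, and neither names withdrawn consent. One follows the list of reasons for termination by the investigator; the other concerns a subject who wishes to stop participating. Protocol 12.3 does not address withdrawn consent either, and protocol 9 lets the SAP modify protocol plans. All of this is correct, and it softens the conflict with the protocol. It does not resolve the conflict inside the SAP, and SAP 4.2 announces no modification.

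Third, the wording may mirror the consent form, which is not available for this review. That possibility is real. It is a reason to cite the requirement, and the fix allows for it.

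Fourth, a woman who reports an exit test has agreed to give the result, and SAP 6.2.4.2 would cover a pregnancy found that way. This is the sensible reading, but SAP 4.2 as worded points the other way.

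Fifth, SAP 4.3 requires missing data to be flagged with a reason, and consent withdrawals appear in the disposition table. Neither reports the excluded events, and it is unclear whether SAP 4.3 covers deliberate exclusions.

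Finally, the analyses are descriptive, no threshold decision is affected, and the numerical illustration measures nothing about this trial. That limits the weight of the point but does not remove it.

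**Conclusion.** The concern holds. Followed literally, SAP 4.2 permits the omission of adverse events and pregnancies recorded before consent was withdrawn. This is broader than the exception in protocol 5.5 and at odds with SAP 6.2.4 and the Safety Population definition. The text allows the omission; it does not show that any occurred or was intended.

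Neither the size nor the direction of any effect can be determined from the documents. On the assumed counts, one or two removals matter little among 100 users and visibly among 20. SAP 1 says early termination left too few subjects for the planned endpoints, so individual women may matter. The correction should be made. Confidence is medium, because the intended meaning and the consent form's terms are unknown.

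**What to change.** Reword SAP 4.2 in one or two sentences to say that:

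- all data collected up to the point of withdrawal are included in the adverse event and pregnancy summaries, whatever the reason for withdrawal;
- data collected afterwards, including the exit interview and exit pregnancy test under protocol 5.5, are included when the subject agreed to provide them and excluded only if she asked otherwise.

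If the consent form or a legal rule requires removal of earlier data, cite it in SAP 4.2, qualify the unqualified statements in SAP 6.2.4.1 and 6.2.4.2 to match, and report the number of subjects removed.

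The cost is a short text change with no new data or analyses. If removal is required, it adds one qualifying sentence in SAP 6.2.4 and one count.
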